### 7.5.3.2 Physical examinations

Physical examinations will be performed according to the schedule summarized in the flow chart of Section 7.1.

# 7.5.3.2.1 Complete physical examination

Complete physical examination includes ECOG performance status assessment, NYHA classification (see Appendix 14.3), height (only at Screening), weight, vital signs (see Section 7.5.3.3), and complete review of body systems.

All clinical signs and regions that can be brought in context with the underlying disease, with the anti-cancer treatment to be administered or with relevant accompanying diseases (if present) should be clinically assessed.

At minimum the following aspects/regions need to be assessed as well:

- General appearance
- Skin (paleness, jaundice, redness/rash, acneiform changes) including clinical assessment of hydration status via hand extensor surface skin turgor
- Hand and feet (signs of hand-foot-skin-syndrome/ hand-foot skin reaction)
- Eyes (accommodation, double images, abnormal sensitivity to light, jaundice)
- Ears, nose, throat (presence of petechial bleeding, gingival bleeding) including inspection of oral mucosa for hydration status
- Head and neck
- Lungs: evaluation of new onset or worsening of pulmonary symptoms, and lung examination
- Heart
- Abdomen (pain, tenderness, peristaltism, ascites, organomegaly)
- Lymph nodes
- Musculoskeletal system and spine
- Lower legs (petechial bleedings, ulcer, signs of thrombosis)
- Neurologic findings

### 7.5.3.2.2 Brief physical examination

Brief physical examination includes ECOG performance status, vital signs (see Section 7.5.3.3), examination of pertinent organ systems, and brief interim history (change of symptoms).

09 FEB 2023 Page: 87 of 151

The examination of pertinent organ systems should investigate at minimum:

- Skin (paleness, jaundice, redness/rash, acneiforme changes) including clinical assessment of hydration status via hand extensor surface skin turgor
- Hand and feet (signs of hand-foot-skin-syndrome)
- Throat (presence of petechial bleeding, gingival bleeding) including inspection of oral mucosa for hydration status
- Lungs: evaluation of new onset or worsening of pulmonary symptoms, and lung examination
- Abdomen (pain, tenderness, peristaltic, ascites, organomegaly)
- Neurologic findings

Other clinical signs and regions might be investigated as well, if clinically indicated.

# **7.5.3.3 Vital signs**

Pulse, blood pressure and temperature will be assessed according to the schedule summarized in the flow chart of Section 7.1. If clinically indicated, it is at the investigator's discretion to perform these measurements more frequently.

### Blood pressure measurement on infusion days

Blood pressure will be measured prior to each copanlisib/placebo dose (no more than 4 measurements) until there are two consecutive results <150/90 mmHg with at least 15 min interval between the measurements, to be able to start copanlisib/placebo infusion (pre-dose). The investigator can consider a medical intervention to maintain blood pressure values appropriate for infusion. The investigator must delay the infusion until blood pressure values are <150/90 mmHg. The patient should rest for 5-10 min before blood pressure is recorded.

• On copanlisib/placebo infusion days: blood pressure will be measured at pre-dose. Blood pressure can be measured during or after copanlisib/placebo infusion if clinically indicated/based on the investigator's discretion.

For details on the management of arterial hypertension, see also Sections 6.4.1 (dose modification) and 6.4.2.3 (treatment of blood pressure increases).

#### 7.5.3.4 12-lead ECG

12-lead ECGs will be performed according to the schedule summarized in the flow chart in Section 7.1. The study number, patient number, visit and the date of the ECG will be noted on every ECG.

The patient should rest for 5-10 min before the ECG is recorded.

The overall interpretation of the ECG (normal/abnormal, clinical relevance) and the ECG findings will be recorded in the source documentation and in the eCRF.

#### 7.5.3.5 Cardiac function

Cardiac function test: echocardiogram or MUGA scan. The method chosen at baseline (i.e. either echocardiogram or MUGA scan) must be used throughout the whole study period. Additional cardiac function tests are required if any signs or symptoms of cardiac dysfunction occur.

09 FEB 2023 Page: 88 of 151

Echocardiogram/MUGA scan should be performed for determination of LVEF.

The study number, patient number, visit and the date of the echocardiogram/MUGA scan are noted on every echocardiogram/MUGA scan.

The overall interpretation of the echocardiogram/MUGA scan and findings will be recorded in the source documentation and in the eCRF.

# 7.5.3.6 ECOG performance status

Grading definitions are given in Appendix 14.2.

# 7.5.3.7 Glucose measurement on copanlisib/placebo infusion days

- On Cycle 1 Day 1: glucose will be measured at pre-dose and post-dose 1 h and 2 h after the end of copanlisib/placebo infusion; and at the end of rituximab infusion. Additional measurements to be performed at the clinic as clinically indicated.
- On subsequent copanlisib/placebo infusion days: glucose will be measured prior to copanlisib/placebo infusion. Additional measurements to be performed at the clinic as clinically indicated.
- On all copanlisib/placebo infusion days: time window of  $\pm$  10 min is allowed for glucose measurements (except for the pre-dose measurement).

# 7.6 Other procedures and variables

# 7.6.1 Biomarker investigations

#### Overview

There will be several parts to biomarker testing in this study:

- 1) tumor-genetic testing of fresh (preferred) or archival tumor tissue, and possibly of circulating tumor DNA isolated from plasma
- 2) non-genetic biomarker testing
- 3) genetic biomarker research

Genetic biomarker research of the whole blood requires separate 'genetic' research consent (optional testing for research). All other analyses are covered by the main ICF.

#### **Biomarker investigations**

The planned biomarker analyses utilize tumor tissue, plasma and blood, and involve the analysis of protein and nucleic acids (i.e., RNA and/or DNA). Details on the collection, processing, storage and shipment of biomarker samples will be provided in separate documents (e.g. sample handling sheets or laboratory manual).

The biomarker results may be reported separately.

### Collection and use of biomarker specimens

Biomarker samplings are not applicable to sites who cannot obtain approval by competent Health Authority.

### **Optional Tumor Tissue**

One or more of the following pre-treatment tumor tissue samples should be collected during Screening when available with the purpose of investigating or identifying biomarkers that

09 FEB 2023 Page: 89 of 151

may be predictive of copanlisib effects/efficacy in NHL and to contribute to better understanding the disease.

- Submission of archival tumor tissue from a biopsy performed within 180 days before signing of the informed consent
- Submission of fresh tissue from a biopsy performed during Screening (between Day -28 and Day -8 prior to the start of study treatment) is highly encouraged when the above is not available.
- In the absence of either of the above, submission of an older archival tumor tissue sample (collected prior to 180 days before study enrollment) is mandatory when available.

A tumor biopsy is also encouraged at the time of progression (optional) to allow investigation of copanlisib resistance. In addition, if a tumor biopsy/excision occurs during the course of the study based on medical need, a sample should be submitted (though no biopsy is required during treatment)

Archival FFPE tissue may be supplied as a block (preferred) or as precut slides. Details on the preparation of slides and number of slides to be prepared as well as detailed guidance on fresh biopsy sample preparation and storage will be described in separate documents (e.g. Sample Handling Sheets or Laboratory Manual)

All tumor tissues may be used as a source of RNA or protein for the study of gene and protein expression. The tumor tissue may in addition be used as a source of tumor DNA for the evaluation of tumor-associated alterations in genes of interest (e.g., PIK3CA and genes associated with NHL).

**Plasma for non-genetic biomarker** analysis: Blood samples will be obtained and used for plasma preparation at the time points as indicated in the study flow chart (see Table 7–1). Plasma may be used to quantify the circulating levels of various proteins.

**Plasma for tumor genetics:** Blood samples will be obtained and used for plasma preparation at the time points as indicated in the study flow chart (see Table 7–1). Plasma may be used as a source of circulating tumor DNA for the evaluation of mutations in tumor-related genes of interest.

Whole blood (only applicable for patients who provided 'genetic' research consent): At Screening, a whole blood sample will be obtained. The blood sample will be used as a source of DNA and gene products for the evaluation factors that are associated with the drug or the pathomechanisms of the disease. Results will be reported under separate cover, if the evaluations are performed.

In addition to the proteins and genes listed above, other biomarkers deemed relevant to gain further knowledge about the pathomechanism of the disease or about the drug (i.e. mode of action or safety of the drug) may be measured, based on newly emerging data from other ongoing trials of these investigational drugs and/or literature data. However, the study sponsors reserve the right not to conduct all or part of the aforementioned biomarker analysis. Data from this biomarker analysis may be correlated with various other data obtained in this study (e.g., clinical efficacy, pharmacokinetics, toxicity).

If a scheduled biomarker sample collection is missed, this should not be regarded as a protocol deviation.

09 FEB 2023 Page: 90 of 151

# 7.6.2 Quality of life questionnaire

No further data collection is required for the QoL questionnaires, and electronic PRO devices will no longer be used.

# 7.7 Appropriateness of procedures / measurements

The efficacy assessments used in this study include those considered standard of care to evaluate objective tumor response rate in patients with iNHL. Although the recently published Recommendations for Initial Evaluation, Staging, and Response Assessment of Hodgkin and Non-Hodgkin Lymphoma: The Lugano Classification (27) strongly support the use of PET-CT for staging and response assessment of routinely FDG-avid histologies, especially in clinical trials, it was decided to use in this study only a CT-based response. CT/MRI-based response remains in fact preferred for histologies with low or variable FDG avidity and in regions of the world where PET-CT is unavailable. Moreover, in trials exploring new agents in multiply relapsed disease where data are lacking regarding PET-CT and where assessment of disease control is more important than likelihood of cure, CT/MRI-based response may also be more relevant.

The safety assessments are appropriate and standard to monitor safety and assess toxicity.

# 8. Statistical methods and determination of sample size

### 8.1 General considerations

Statistical analyses will be conducted by or under the supervision of the sponsor's study statistician, except for the analysis of biomarker data, which will be performed by or under the direction of the sponsor's genomics and biomarker statistical expert. Statistical analyses will be performed using Statistical Analysis System (SAS); the version used will be specified in the statistical analysis plan (SAP).

Further details on the statistical analyses including handling of missing data will be provided in the SAP that will be approved before database release.

### 8.2 Analysis sets

The statistical analysis sets are defined as follows:

Full analysis set (FAS): all patients randomized.

Safety analysis set (SAF): all FAS patients with at least one intake of copanlisib/placebo or rituximab.

All patients with valid PK data will be included in the evaluation of PK concentrations and parameters.

The efficacy variables will be analyzed in the FAS.

The SAF will be used for the analyses of the safety variables. The FAS will be used for the display of all other variables.

09 FEB 2023 Page: 91 of 151

#### 8.3 Variables

# 8.3.1 Efficacy variables

Disease progression (PD) in the context of statistical efficacy evaluation is considered to be radiological progression, as assessed by central review. For WM patients without radiologically measureable disease, clinical progression will be used.

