An end-of-treatment (EOT) visit will be performed no later than 7 days after the decision is made to discontinue study treatment. Following completion of the EOT visit, patients will enter either the Safety follow-up or the Active follow-up period, if applicable. In both cases, the Safety follow-up visit will take place 30 days (window of +5 days allowed) after the last administration of study treatment.

Patients who discontinue study treatment because of PD will enter the Safety-follow up period and patients who discontinue study drug for reasons other than PD will enter the Active follow-up period (which also serves as a Safety follow-up), except for patients who object to follow-up data collection. The patients in the Active follow-up will have tumor assessments performed locally as outlined in this protocol until the end of the Active follow-up period, defined as when either PD is documented or a new anti-tumor treatment is administered, whichever occurs first. During the Active follow-up period, serious adverse events (SAEs) and AEs assessed as related to study procedures by the investigator will be reported. AE pages of the electronic Case Report Form (eCRF) and the SAE Form should be completed in the usual manner and forwarded to the applicable sponsor's PV department.

All patients will be followed off study for overall survival at 3-monthly intervals during the Survival follow-up period (up to 7 years after the last patient started study treatment), except for patients who object to follow-up data collection. During this period, patients are not considered to be "on-study".

Safety evaluations will be done at Screening, on the first day of study treatment administration (Cycle 1 Day 1), at each clinic visit during the treatment, and at the Safety follow-up visit. NCI-CTCAE version 4.03 will be used to grade toxicities/AEs. Doses may be delayed or reduced in

09 FEB 2023 Page: 30 of 151

cases of clinically significant hematological or other toxicities that are possibly, probably or definitely related to study treatment. The dose modification levels and the delay of copanlisib/placebo administration will follow pre-defined rules (see Section 6.4.1).

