### 5.2.1.1 Withdrawal of study treatment

Patients *must* be withdrawn from the study treatment for the following reasons:

- At their own request or at the request of their legally acceptable representative. At any time during the study and without giving reasons, a patient may decline to participate further. The patient will not suffer any disadvantage as a result. Patients who withdraw consent from treatment will still participate in the Safety, Active or Survival follow-up unless they object to follow-up data collection (see Section 11.2).
- If, in the investigator's opinion, continuation of the study would be harmful to the patient's well-being.
- Disease progression as defined in the Lugano Classification and, for patients with WM, according to the Owen Criteria.
- Occurrence of unacceptable toxicity.
- CTCAE Grade 4 arterial hypertension.

09 FEB 2023 Page: 39 of 151

- Persistent occurrence of post-infusion blood glucose > 500 mg/dL based on laboratory analysis which occurred at the lowest copanlisib/placebo dose level despite optimal glucose lowering therapy (after at least one cycle of treatment).
   Definition of persistent occurrence is based on repeated post-infusion blood glucose laboratory analysis taken at different time during the whole cycle of treatment.
- CTCAE Grade 4 dermatologic toxicity.
- CTCAE Grade ≥3 (or recurrent Grade 2) non-infectious pneumonitis.
- Drug-induced pancreatitis.
- Development of a malignancy other than indolent B-cell NHL. New malignancy will be reported as an SAE.
- Start of a new anti-cancer regimen.
- The patient does not tolerate copanlisib/placebo dose of 30 mg.
- The patient presents during further testing a positive viral load when initial HBV DNA and/or HCV RNA testing was negative.
- Severe allergic reaction to test drug (such as CTCAE Grade 3 or 4 hypersensitivity reaction).
- Severe (life-threatening) reaction to rituximab infusion despite optimal supportive treatment.
- Patient lost to follow-up.
- Substantial non-compliance with the requirements of the study.
- Delay in test drug administration due to toxicities for > 28 days (a delay of test drug dosing due to reasons other than toxicity is not included in this definition). Except, in case of delays due to reactivation of CMV where delays could be up to 2 months.
- Development of any intercurrent illness or situation which, in the judgment of the investigator, may affect assessments of clinical status and study endpoints to a relevant degree.

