- The first IV (and oral, if indicated, per Imaging Manual) contrast enhanced CT/MRI scans of neck, chest, abdomen and pelvis must be performed at Screening (including WM patients). Corticosteroids must stopped or reduced to the allowed dose (≤ 15 mg of prednisone or equivalent) at least 7 days before performing the screening CT/MRI (if a patient is on chronic corticosteroid therapy, corticosteroids should be de-escalated to the maximum allowed dose before the screening). During treatment and Active follow-up periods, tumor scans will be done with the same modality every 8 weeks (± 7 days) during Year 1, every 12 weeks (± 7 days) during Year 2, and every 24 weeks (± 7 days) during Year 3 and onwards, starting from Cycle 1 Day 1. CT/MRI scans are not required at the EOT visit if the patient discontinued due to PD which has been radiologically evaluated within the 4 weeks preceding EOT. Tumor scans will be done until PD is documented or new antitumor treatment is administered. MRI shall be performed instead of CT when local regulations do not permit the use of CT as requested per protocol schedule (see Section 7.3.2). WM patients who do not have radiologically measurable lesion at Screening will not have further radiological assessments as per protocol. Their tumor response will be measured only by laboratory/clinical tests. WM patients who have radiologically measurable lesion at Screening will continue having radiological assessments and, in addition, will have laboratory tests performed on the same days (see footnote r, and Sections 7.1.2.3 and 7.3.3). No central independent blinded review will be done.
- As of Amendment 12, no further data collection is required for the QoL questionnaires.
- Bone marrow biopsy is mandatory at Screening and will be sent to central pathology review after local bone marrow assessment. If the baseline biopsy is positive for lymphoma infiltration at Screening, it will be mandatory to perform it again to confirm the first CR, and also at the investigator's discretion if clinical evaluation leads to suspicion of bone marrow infiltration without further radiological findings. No central review of bone marrow biopsy will be performed during treatment or Active follow-up.
- Only for patients affected by LPL/WM: Serum protein electrophoresis, immunofixation and serum quantitative IgM test to be performed at Screening. Serum or plasma viscosity to be tested at Screening only if hyperviscosity syndrome is suspected.

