# 7.3.2 Radiological tumor assessments

Radiologic tumor assessments will include neck, chest, abdomen and pelvis, and will be evaluated locally at the study site.

The first radiological (IV [and oral, if indicated, per Imaging Manual] contrast-enhanced CT/MRI) tumor assessment will be performed at Screening (including WM patients). Corticosteroids must be stopped or reduced to the allowed dose (≤ 15 mg of prednisone or equivalent) at least 7 days before performing screening CT/MRI (if a patient is on chronic corticosteroid therapy, corticosteroids should be de-escalated to the maximum allowed dose before the screening). Scans done up to 28 days prior to first dose can be used as baseline studies. The method chosen at baseline must be the same throughout the study. MRI shall be performed instead of CT when local regulations do not permit the use of CT as requested per protocol schedule.

During the treatment phase as well as during the Active follow up period, radiological (IV [and oral, if indicated, per Imaging Manual] contrast-enhanced CT/MRI) tumor assessment will be performed every 8 weeks ( $\pm$  7 days) during Year 1, every 12 weeks ( $\pm$  7 days) during Year 2, and every 24 weeks ( $\pm$  7 days) during Year 3 and onwards. CT/MRI scans are not required at the EOT visit if the patient discontinues due to PD which has been radiologically confirmed within the 4 weeks preceding EOT. Central independent blinded review of tumor scans will not be performed.

At each tumor assessment during the course of the study (from baseline to EOT and during Active follow up if applicable) radiological measurement of spleen vertical length (from cranial to caudal) must be performed and reported.

The response assessment will be done according to the Lugano Classification. For patients with WM, additional criteria apply (see Section 7.3.3). Detailed instructions on tumor assessment are provided in Appendix 14.4.

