# 8.3.1.1 Primary efficacy variable

 Progression-free survival (PFS), defined as the time (in days) from randomization to PD or death from any cause (if no progression is documented). The actual date of tumor assessments will be used for this calculation. PFS for patients without PD or death at the time of analysis will be censored at the date of their last tumor evaluation. PFS for patients who have neither tumor assessments nor death after baseline will be censored at Day 1.

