## Response criteria in patients affected by Waldenström macroglobulinemia (WM):

Complete Response	
 
Absence of serum monoclonal IgM by immunofixation AND normal serum IgM level
 
Complete resolution of extramedullary disease
 
				
	Normal bone marrow				
Very Good Partial	
 
IgM M protein still detectable by immunofixation BUT ≥ 90% reduction in serum IgM level from baseline
 
				
Response	Complete resolution of extramedullary disease				
	No new signs/symptoms of active disease				
Partial Response	• IgM M protein still detectable by immunofixation BUT ≥ 50% and < 90% reduction in serum IgM level from baseline				
	Reduction in extramedullary disease				
	No new signs/symptoms of active disease				
Minor Response	• IgM M protein still detectable by immunofixation BUT ≥ 25% and < 50% reduction in serum IgM level from baseline				
	No new signs/symptoms of active disease				
Stable Disease	
 
IgM M protein still detectable by immunofixation BUT < 25% reduction and < 25% increase in serum IgM level from baseline
 
				
	
 
No new signs/symptoms of active disease
 
				
Progressive Disease	
 
≥ 25% increase in serum IgM level from nadir confirmed by a repeat assessment (an absolute value increase of 5 g/L is required if IgM level is the only criterion)
 
OR
 
				
	Progression in clinical features (signs/symptoms) attributable to disease				
	After Complete Response:				
	Reappearance of IgM M protein				
	OR				
	Recurrence of bone marrow involvement, extramedullary disease, symptoms attributable to disease				

Source: Adapted from Owen RG et al, 2013 (35)

09 FEB 2023 Page: 149 of 151

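### For Waldenström (WM) patients with a measurable lesion, progression met only on the Owen criteria ends treatment and scheduled scans but is not a counted event, so follow-up PFS, TTP and DOR can be censored at progression (probably a small effect)

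*Protocol*

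**What the plan says.** **Analysis definition.** Protocol Section 8.3.1: "Disease progression (PD) in the context of statistical efficacy evaluation is considered to be radiological progression, as assessed by central review". The next sentence gives the only exception: "For WM patients without radiologically measureable disease, clinical progression will be used". WM patients who do have a lesion stay under the radiological rule.

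**Treatment definition.** Section 5.2.1.1 lists as a mandatory reason to stop treatment: "Disease progression as defined in the Lugano Classification and, for patients with WM, according to the Owen Criteria". It makes no distinction by whether a lesion is present. Appendix 14.4 lets Owen progression be met without imaging, either by a 25% or greater "increase in serum IgM level from nadir confirmed by a repeat assessment" (with an absolute rise of 5 g/L if IgM is the only criterion) or by clinical features attributable to the disease.

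**What follows progression.** Section 4: "Patients who discontinue study treatment because of PD will enter the Safety-follow up period". Active follow-up, where tumor assessments continue, is for patients who stop for other reasons. The CT/MRI footnote to Table 7-1: "Tumor scans will be done until PD is documented or new antitumor treatment is administered".

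**End-of-treatment scan.** Section 7.3.2: "CT/MRI scans are not required at the EOT visit if the patient discontinues due to PD which has been radiologically confirmed" within the preceding 4 weeks. The Synopsis and Section 4 also say *confirmed*. The Table 7-1 footnote and Section 7.1.2.4 instead waive the scan when the progression was radiologically *evaluated* in that window.

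**Censoring.** Section 8.3.1.1: "PFS for patients without PD or death at the time of analysis will be censored at the date of their last tumor evaluation". Section 8.3.1.2 has matching rules for TTP and DOR, and it starts DOR on CR, VGPR, PR or MR.

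**Follow-up analyses.** SAP Supplement 1.0, Section 6.2, plans PFS, TTP and DOR by independent and by investigator assessment. Supplements 2.0 and 3 repeat these analyses.

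**The concern.** One patient is handled under two definitions of progression. Owen progression ends treatment and scheduled imaging, but the analysis waits for a radiological event that is no longer being looked for on schedule. If none is recorded and no qualifying death follows, the patient is censored at the last tumor evaluation. WM laboratory tests fall on scan days, so that date will often be the day the Owen criteria were met, or close to it.

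Protocol Section 8.4.2.1 assumes that censoring of patients without an event is non-informative. Censoring caused by progression is not. In these patients it lengthens Kaplan-Meier estimates of PFS, TTP and DOR.

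DOR has a further inconsistency. VGPR and MR exist only in the Owen criteria, so the clock can start on an Owen response that an Owen progression cannot stop.

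Reporting is also at stake. If the investigator-assessed analyses count Owen progression and the independent ones do not, the two results can differ by definition, and a reader could take that for disagreement between readers.

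**Working it through.** **1. The plan's own figure.** Table 8-1 gives 89.5% power for 190 events, HR 0.61, 2:1 allocation and one-sided alpha 0.025. Schoenfeld's formula returns 89.47%, so the figure reproduces. The point does not dispute it.

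**2. Path of a WM patient with a lesion and Owen-only progression.**

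| Step | Source | Result |
|---|---|---|
| IgM rise or clinical features meet Owen PD | Appendix 14.4 | no radiological PD |
| Treatment stops | 5.2.1.1 | mandatory |
| Follow-up type | Section 4 | Safety, not Active |
| Scheduled scans | Table 7-1 footnote | end |
| End-of-treatment scan | 7.3.2 against 7.1.2.4 and Table 7-1 | may or may not be due |
| Counted event? | 8.3.1 | no |
| PFS, TTP, DOR | 8.3.1.1, 8.3.1.2 | censored at last tumor evaluation unless radiological PD or a qualifying death is recorded |

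The end-of-treatment row matters. Under *confirmed*, a recent scan without radiological progression does not waive the final scan. Under *evaluated*, it may.

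**3. Upper limit on numbers.** Table 8-1: 458 - 370 = 88 patients outside FL and MZL, and 88/458 = 19.2%. This group is SLL plus LPL/WM. The number of WM patients with a lesion is not given.

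**4. Effect on the FAS hazard ratio.** The following are assumptions, not figures from the documents: m = 10 to 40 WM patients with a lesion; Owen-only share p of 25% or 50%, differing by arm; share r rescued by a final scan or death of 0 or one half; exponential PFS. With f = m/458 (2.18% or 8.73%), approximately:

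HR read = 0.61 × [1 - f·pT·(1 - r)] / [1 - f·pC·(1 - r)]

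Example with m = 40, r = 0, pT = 0.25, pC = 0.50: 0.61 × (1 - 0.0218)/(1 - 0.0437) = 0.624.

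| m | r | pT 0.25, pC 0.50 | pT 0.50, pC 0.25 |
|---|---|---|---|
| 10 | 0 | 0.613 | 0.607 |
| 40 | 0 | 0.624 | 0.596 |
| 10 | 0.5 | 0.612 | 0.608 |
| 40 | 0.5 | 0.617 | 0.603 |

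If pT = pC the ratio of brackets is 1 and the HR stays 0.61.

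SE(log HR) = sqrt[1/(190 × 2/3 × 1/3)] = 0.154. The largest shift by formula is ln(0.624/0.61) = 0.023, or 0.15 SE.

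A simulation used 1,500 trials, 2:1 allocation, medians of 23 and 14 months, assumed accrual over 46 months, an assumed dropout hazard of 0.012 per month, and a cut at 190 counted events. With 40 patients and no rescue it gave 0.623 and 0.593. With half rescued it gave 0.613 and 0.603. The value 0.593 is a shift of -0.028, or 0.18 SE, slightly beyond the formula. The Monte Carlo SE of log HR was 0.004. A fair range is therefore about 0.59 to 0.62.

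**5. Uncounted progressions per 190 counted events.** 190 × x/(1 - x), with x = f·p·(1 - r). For r = 0 this runs from 1.04 (m = 10, p = 25%) to 8.68 (m = 40, p = 50%). For r = 0.5 it runs from 0.52 to 4.24.

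**6. Effect within the subset.** If a share p of events is not counted, the apparent exponential median is the true median divided by (1 - p). With the planning medians of 14 and 23 months, used only for illustration, p = 25% gives 18.7 and 30.7, and p = 50% gives 28 and 46. Estimates confined to these patients are far more sensitive than the FAS result.

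**The case against.** **The detail may sit elsewhere.** Protocol Section 8.1 defers analysis detail to the SAP. Section 8.4.2.1 promises sensitivity analyses with other event and censoring rules, to be set out there. Main SAP v6.0 was not supplied, and the supplements are short additions to it. This stands as a limit: a reader might infer that the plan as a whole never deals with this case, and the documents do not support that. But a general promise does not name this case, and Section 8.3.1 is not silent. It states a rule, and that rule produces the censoring.

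**The investigator-assessed analyses may already count it.** Section 4 has sites assess WM by Owen, so this is plausible. Supplement 1.0, Section 6.2, does not define progression for those analyses, so it remains an inference.

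**A centrally read event can deliberately be stricter than the rule for stopping treatment.** That is a legitimate design choice, and the reason to leave the primary definition alone. It does not make the censoring non-informative, and it does not explain why DOR starts on one set of criteria and ends on another.

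**The end-of-treatment scan could catch these patients.** Only if the scan is done and shows radiological progression. The waiver wording conflicts between sections, so one can assume neither that the scan is always due nor that it is always waived.

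**The size rests on assumed inputs.** Correct. The patient count, the shares and the rescue fraction are all assumed, and no passage suggests that the shares differ by arm. TTP and DOR are supportive only (Section 8.4.2.2).

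**Conclusion.** The point holds for the current protocol text and the follow-up analyses, as a minor one. Read literally, Section 8.3.1 can censor PFS, TTP and DOR at progression in WM patients with a lesion, and DOR mixes two criteria. No supplied text says which analysis, if any, counts Owen-only progression in them.

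The FAS effect is probably small: about 0.59 to 0.62 around a hazard ratio of 0.61 under the assumed inputs, and none if the Owen-only share is equal by arm. The subset-level time estimates could be lengthened more.

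A reader might infer that the primary result is unsafe or that power was lost. The documents support neither. The largest shift is under a fifth of a standard error even with 40 affected patients and a twofold imbalance between arms. Power is protected because the analysis waits for at least 190 counted events. The US test of PFS in FL plus MZL contains no WM patients, and OS does not depend on progression. The protocol text in force at the primary analysis was not supplied either, so nothing here is a finding about how that analysis was run.

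**What to change.** Leave the primary definition and result unchanged. In the follow-up SAP supplement:

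- Add a sensitivity analysis of PFS, TTP and DOR, outside the confirmatory sequence. It should keep the same radiological reader rule for all patients as the analysis it is compared with, and change one thing only: for WM patients with a measurable lesion, Owen progression per Appendix 14.4 also counts as PD. One reader rule matters because central image review ended with Amendment 12. Changing the reader for WM patients alone would make any difference impossible to attribute to Owen progression.
- Date these events by one stated rule. For an IgM rise, for example, use the first assessment meeting the criterion, once the repeat confirms it.
- State that investigator-assessed PFS, TTP and DOR count Owen progression for WM patients.
- Report by arm the number of WM patients with a lesion and the number with Owen-only progression.

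Separately, reconcile the end-of-treatment scan waiver (*confirmed* in the Synopsis, Section 4 and Section 7.3.2; *evaluated* in the Table 7-1 footnote and Section 7.1.2.4).

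Cost: a few sentences, one derivation and one table. The protocol already schedules IgM, electrophoresis and immunofixation on tumor-assessment days (Section 7.1.2.3). The downside is that some sensitivity events would rest on local laboratory or clinical data without central adjudication, and the analysis is post hoc and should be labelled so. If main SAP v6.0 already states the rule, a cross-reference to it would replace the new definition.
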